## **Summary**

Dental caries (tooth decay) is common among elders in Hong Kong and worldwide, placing heavy burden on the dental care services. There is an urgent need to develop effective and practical management approaches to improve the dental caries situation in the elders, especially among those living in residential care homes whose dental caries status is amongst the worst. The main objective of this study is to compare the effectiveness and cost-effectiveness of 4-monthly application of 10% povidone iodine solution followed by 5% sodium fluoride varnish with those of annual application of 38% silver diammine fluoride solution on the prevention of new dental root caries in elders. A secondary objective is to compare the effectiveness of the two interventions mentioned above on arresting (halting the progression) active root surface caries in the elders, thus avoiding the need for placing dental restorations.

This proposed study is a randomized double-blind controlled clinical trial with 24-month follow-up. A total of 332 elders aged 60 years or above living in residential homes or attending long-term care facilities in different districts in Hong Kong will be recruited. This sample size is sufficient for appropriate statistical analysis of non-inferiority with power set at 90% and allowing for a 20% dropout. Baseline clinical examination will be conducted by a single calibrated examiner in the homes using an intra-oral LED light, dental mirrors and probes. Subjects will be randomly allocated to one of the two study groups: 1) positive control - receive annual application of 38% silver diammine fluoride solution; and 2) test - receive application of 10% povidone iodine solution followed by application of 5% sodium fluoride varnish every 4 months. Follow-up examinations will be carried out after 12 and 24 months by the same blinded examiner to assess the clinical outcomes, i.e. whether new dental caries has developed and whether the active root surface caries lesions found at baseline have become arrested (hardened). Results of this study will provide the much needed evidence to guide the dental professionals in Hong Kong and worldwide in deciding on the most appropriate intervention for the prevention and management of dental caries in the older adults, especially those living in institutions.

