### **3.3. The baseline and follow-up examinations**

The baseline and follow-up examinations after 12 and 24 months will be carried out in the residential home by a single trained examiner. A portable dental chair, an intra-oral LED light, disposable dental mirrors and CPI probes will be used in the examination.

For each tooth that is not indicated for extraction, status of its crown and its root will be assessed and recorded separately. Caries diagnosis is based on visual and tactile inspection. No radiograph will be taken. Plaque and food debris that obscures visual inspection of the tooth surfaces will be removed. Four surfaces (mesial distal, buccal and lingual) per tooth will be examined and the status will be recorded using the following codes which basically follow the criteria recommended by the International Caries Detection and Assessment System (ICDAS II) Coordinating Committee (2009).

The oral hygiene status of the subject will be assessed and recorded by using the Visible Plaque Index (Ainamo & Bay, 1975). The presence or absence of visible plaque will be recorded on four surfaces (mesial, distal, buccal and lingual) per tooth.

The gingival status of the subject will be assessed and recorded using by the Gingival Bleeding Index (Ainamo & Bay, 1975). The presence or absence of bleeding within 10 seconds after running a probe across the gingival margin will be recorded on four surfaces (mesial, distal, buccal and lingual) per tooth.

Other information that will be recorded included whether the subject normally wears a removable partial denture or not, and the subject's general health status and medications that affect saliva flow rate.

The same examiner will carry out all the baseline and follow-up examinations without knowing the study group assignment of the subjects. It has been shown that good intra-examiner reproducibility can be achieved after training (Tan et al., 2010) and a random sample of 10% of the subjects will be re-examined during each examination to monitor intra-examiner reproducibility.

At the examinations, the subjects will be asked to report on their oral hygiene practices, use of fluoridated toothpaste and other topical fluoride agents, and use of dental services during the study period.

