### **3.4. Interventions**

Oral health education talk and instructions on how to keep good oral hygiene will be provided at baseline and every year to all the elders in the selected residential homes. Standard fluoride toothpaste with 1000-1500 ppm fluoride will be provided free to all the elders in the selected residential homes over the 24-month study period.

After the baseline examination, subjects satisfying the inclusion criteria of the study will be stratified into two groups according to the number of natural teeth in their mouth, those with 12 or fewer teeth and those with 13 or more teeth. The subjects will then be assigned to one of the two study groups by a research assistant using a block randomization method with a block size of 6. The stratified randomization procedure will help to ensure that

the numbers of teeth involved in the two study groups are balanced. The group assignment of the study subjects will be concealed and placed in a sealed envelope, and will not be made known to the examiner who evaluate the study outcomes.

The interventions for the two study groups will be provided by other dentists and are described below:

Group 1 – plaque on the root surfaces of all teeth in the subject’s mouth will be removed by a small brush and a 38% SDF solution (Saforide, Toyo Chemical, Japan ) will be applied onto the root surfaces using a microbrush/applicator. This will be repeated every year.

Group 2 – plaque on the root surfaces of all teeth in the subject’s mouth will be removed by a small brush and a 10% povidone iodine solution (Betadine, Mundipharma, Switzerland) will be applied, then followed by application of a 5% sodium fluoride varnish (Duraflor, Medicom, Canada) using a microbrush/applicator. This will be repeated every 4 months.

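### Does calling the trial double-blind, when only the examiner is described as masked, call for a change to the plan?

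*Protocol*

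**What the plan says.** The Summary gives the design label: "This proposed study is a randomized double-blind controlled clinical trial with 24-month follow-up". Three statements then say who is masked.

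- Summary, on follow-up: "Follow-up examinations will be carried out after 12 and 24 months by the same blinded examiner to assess the clinical outcomes".
- Section 3.3: "The same examiner will carry out all the baseline and follow-up examinations without knowing the study group assignment of the subjects".
- Section 3.4, after describing concealment of the assignment in a sealed envelope: it "will not be made known to the examiner who evaluate the study outcomes".

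Section 3.4 also separates treatment from assessment: "The interventions for the two study groups will be provided by other dentists". In Group 1 these dentists apply a single solution, and "This will be repeated every year". In Group 2 they apply povidone iodine, "then followed by application of a 5% sodium fluoride varnish (Duraflor, Medicom, Canada) using a microbrush/applicator", and "This will be repeated every 4 months".

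The Protocol describes no placebo, dummy application or sham visit. It does not say whether subjects are told their group.

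**The concern.** Double-blind suggests that at least two parties are unaware of the assignment. The Protocol names only one. The treating dentists cannot be the second, since they handle different products in each arm. The subjects are an unlikely second, since the arms differ in the number of agents and in how often they are applied. On this reading the trial as described is examiner-blind, and the Summary overstates the design.

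Two things could be at stake. A report that carried the label forward could lead readers to credit the trial with protection against performance bias that the methods do not describe. Also, the examiner scores by sight and touch, so that mask has to hold. Section 3.3 has subjects report their use of topical fluoride and dental services at the same examinations, which might seem to offer a way for the examiner to learn the arm.

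**Working it through.** The Protocol gives no figure to reproduce. The check compares the label with each masking statement and counts applications from the stated schedules.

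**Who is masked, party by party**

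| Party | What the Protocol says | Reading |
|---|---|---|
| Outcome examiner | Masked, in the Summary, 3.3 and 3.4 | Clear and consistent |
| Treating dentists | Apply one product or two, by group (3.4) | Cannot be masked |
| Subjects | Nothing either way | Open, but doubtful |

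The sealed envelope in section 3.4 does not settle the subjects' row. It most naturally means allocation concealment, and the examiner is the only person that sentence names as kept unaware.

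**Application dates.** Assume a first application at baseline and none at month 24.

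- Group 1, yearly: months 0 and 12, so 2 applications.
- Group 2, every 4 months: months 0, 4, 8, 12, 16 and 20, so 6 applications.

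If one is also given at month 24, the counts are 3 and 7. In both cases months 4, 8, 16 and 20 belong to Group 2 only, which is 4 dates. The difference in schedule is part of the comparison that section 2 sets out to make, so it is not itself a fault.

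**Does the schedule reach the examiner?** Follow-up examinations are at months 12 and 24 (section 3.3). None of the four Group 2-only dates is an examination date, and other dentists give the applications. The unequal schedule could tell a subject which arm they are in. It does not by itself tell the examiner.

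**Do the interview questions reach the examiner?** Section 3.3 does not say that the examiner asks them. Both arms receive a professionally applied fluoride product, and dentists from the non-governmental organisations also treat these subjects (section 3.1). An answer about fluoride or dental visits therefore need not identify the arm.

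**What depends on the label?** The sample size in section 3.2 uses a margin of 0.8 surface, a standard deviation of 2.0 and 90% power. The tests in section 3.5 are a two-sample t-test and a two-level survival analysis. None of these uses the word double-blind, and nor does any instruction to staff.

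**The case for a change.** The case for a change is that the mismatch is on the face of the document and costs one term to correct. Readers judge performance bias partly from the blinding label. Who is masked is a matter of trial conduct, so it cannot be left to an analysis plan. If the sponsor meant that subjects are masked as well, the Protocol should say how.

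Much of this stands. The label is not supported by the methods, the treating dentists cannot be masked as described, and nothing in the text supports masking of subjects.

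Two parts do not stand. First, it goes too far to say that the design lacks subject masking. Double-blind can ordinarily mean subjects plus examiner, in which case the dentists' knowledge does not contradict it. The Protocol is silent on what subjects are told, and the consent material is not in the text at hand. The unequal schedules make subject masking doubtful but do not disprove it. Second, a safeguard around the interview questions would answer a leak that the document does not show. Who asks which question, and when, is detail for a visit manual. Having someone other than the examiner ask would also assume that other staff attend the examinations, which the Protocol does not state.

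**Conclusion.** The observation is accurate, but it is a labelling slip and the plan need not change. The Summary uses a looser term than sections 3.3 and 3.4, and those sections govern what is done. They state correctly the one mask on which both clinical outcomes rest: new root caries and arrest of active lesions, each scored by a single examiner who does not know the group.

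The size is one word in the Summary. No error rate, power figure or estimate moves, and no bias can be quantified or given a direction from the document. The difference of 2 against 6 applications (or 3 against 7) shows why subject masking is doubtful. It does not measure any harm to the result.

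This rests on two assumptions: that examiner masking is carried out as written, and that the interview answers in section 3.3 do not reveal the arm. Nothing in the Protocol contradicts either. Whoever writes the report can name the masked party from sections 3.3 and 3.4 without an amendment.

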## 1. Background

With ageing of the population in most of the economically well-developed areas, tooth decay in the elders has become an important dental public health issue and a heavy burden on the oral health care system. The latest Hong Kong territory-wide oral health survey conducted by the government in 2011 found that 48% of the 65-74 year-old community-dwelling elders had untreated dental caries and 25% of them had root surface caries (Department of Health, 2013). Furthermore, the same survey found that the dental caries situation of the elders who lived in residential care homes or attended long-term care facilities was worse. The institutionalized elders are a high risk group for dental caries in Hong Kong as well as in other countries (Chalmers et al., 2002).

Untreated tooth decay can lead to pain and loss of teeth, and affect general health. Thus, there is an urgent need to develop effective preventive and management measures to improve the dental caries situation among the elders, especially those living in residential care homes. The Hong Kong government financially support non-profit-making non-governmental organizations (NGO) to establish dental outreach teams to provide on-site basic dental care services to the elders who are receiving long-term care. At present, there are around 20 NGO dental outreach teams serving over 30,000 elders in most of the residential care homes throughout Hong Kong. The dental outreach teams, consisting of dentists and dental assistants, bring along hand instruments and portable dental equipment to the residential homes and provide on-site dental examination, oral health education, prevention, scaling and simple dental restorations (Lo et al., 2004). The services of the outreach dental teams follow a general protocol, and are coordinated and monitored by the government Department of Health.

In a recent systematic review by Gluzman and co-workers (2013), eight preventive agents for preventing dental root caries in older adults were identified. In the conclusion, they recommended that the best choice for primary prevention of root caries was annual application of 38% SDF solution while that for secondary prevention of root caries, i.e. arresting active lesions, was professional application of 5% NaF varnish every 3 months.

In a randomized clinical trial with 3-year follow-up conducted among 306 elders living in 21 residential homes in Hong Kong (Tan et al., 2010), it was found that compared to the controls who only received regular oral hygiene instructions, annual topical application of 38% SDF solution could reduce development of new root caries by 71%. The same study also found that application of 5% NaF varnish every 3 months could prevent root caries as well but the prevented fractions were lower than that of SDF solution. It was also found that presence of visible plaque on root surface was a significant risk factor for dental caries, highlighting the need for good plaque control (Tan & Lo, 2014).

Povidone iodine is a newer antiseptic agent for dental use with clinical evidence showing that it is able to inhibit the activities of acidogenic bacteria including (Evans et al., 2015). In a controlled clinical trial on 30 children with severe early childhood caries, it was found that application of 10% povidone iodine every 3 months significantly reduced the amount of *Streptococcus mutans* and caries development over the 12-month study period (Simratvir et al., 2010). Whether the caries prevention effect of fluoride varnish can be enhanced by regular use of an effective anti-plaque agent such as povidone iodine needs to be assessed by conducting randomized clinical trials.

## **2. Objectives of the study**

1. The primary objective is to compare the effectiveness and cost-effectiveness of 4-monthly application of 10% povidone iodine solution followed by 5% NaF varnish with those of annual application of 38% SDF solution, used as a positive control, in preventing new dental root caries in elders who live in residential homes or attend long-term care facilities..
2. The secondary objective is to compare the effectiveness and cost-effectiveness of the above two methods in arresting active root surface caries among these elders.

### **Null hypotheses to be tested:**

1. In this non-inferiority randomised controlled trial, the primary hypothesis to be tested is that 4-monthly application of 10% povidone iodine solution and 5% sodium fluoride varnish is at least not appreciably worse than a 38% SDF solution in preventing new dental root caries development over a 24-month period. The primary outcome measure is the development of new root surface caries lesions in the teeth of the elders.
2. The secondary hypothesis to be tested is that 4-monthly application of 10% povidone iodine solution and 5% sodium fluoride varnish is at least not appreciably worse than a 38% SDF solution in arresting active root caries over a 24-month period. The secondary outcome measure is the conversion of active (soft/demineralized) root surface caries lesions to inactive (hard/remineralized) lesions.

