#### **3.2. Sample size**

This non-inferiority trial aims to compare the caries preventive effect of applications of 38% SDF solution and that of combined 10% povidone iodine solution and 5% NaF varnish. A non-inferiority margin of 0.8 surface for the difference in the mean number of new caries surfaces over the 24-month study period is considered not clinically significant. The estimated sample size is based on the lower limit of the 2-sided 95% confidence interval for the difference set above the non-inferiority margin and the statistical power of the study being set at 90% ( $\beta=0.10$ ). The estimated standard deviation is 2.0, based on the results of a previous clinical trial conducted in Hong Kong (Tan et al., 2010). Using the statistical power analyses software, G\*Power (version 3.1.7; Franz Faul, Universität Kiel, Kiel, Germany), the total required number of elders in each group is calculated to be 133. Allowing for a drop-out rate of 20% in this 24-month study, an initial sample size of 166 subjects in each group or a total of 332 subjects is needed.

With a total sample size of 332 subjects and an estimated mean number of one untreated early/shallow root caries lesions per subject (Department of Health, 2013), there will be 332 root caries lesions in total or 166 lesions in each study group for caries arrest treatment. With this sample size, there is approximately 85% power that an absolute 15% difference in dental caries arrest rates between two groups can be shown to be statistically significant at the 5% level using Chi-square test when the overall success rate of the caries arrest treatment is around 80%.

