### **3.5. Statistical analysis**

The collected data will be entered into a computer and analyzed using the software SPSS for Windows version 20. T-test and Chi-square test will be used, as appropriate, to assess the differences in the distribution of age, gender, denture wearing, number of remaining teeth, number of active caries lesions, oral hygiene practice and status, and gingival status at baseline between the two study groups.

The number of root surfaces with new caries found at each follow-up examination will be calculated. Two-sample t-test test will be used to find out if there are statistically significant differences between the two study groups in the number of tooth surfaces that have developed new dental caries. Both intention-to-treat and per protocol analysis will be performed to compare the effectiveness and efficacy of the two study preventive methods.

Two-level, tooth surface and subject, survival analysis will be used to assess the rates of arrest of active root surface caries in the two study groups (Wong et al. 2005). The statistical significance level for all tests will be set at 5%.

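### The hypotheses section labels non-inferiority as the null, contrary to the basis of the primary sample size, and section 3.5 names only a test of difference, so a non-significant result could pass as non-inferiority

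*Protocol*

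**What the plan says.** The hypotheses section of the protocol (under section 2) is headed "Null hypotheses to be tested" and has two numbered items. The primary item says that the povidone iodine and varnish regimen "is at least not appreciably worse than a 38% SDF solution in preventing new dental root caries development over a 24-month period". The secondary item says that it "is at least not appreciably worse than a 38% SDF solution in arresting active root caries over a 24-month period". No alternative hypothesis is stated for either outcome.

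Section 3.2 gives "A non-inferiority margin of 0.8 surface for the difference in the mean number of new caries surfaces over the 24-month study period". The primary sample size is "based on the lower limit of the 2-sided 95% confidence interval for the difference set above the non-inferiority margin", with 90% power, SD 2.0 and 133 per group before drop-out. For arrest, section 3.2 gives no margin. It states the power to show a 15-point difference in arrest rates by a chi-square test.

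Section 3.5 plans a two-sample t-test for significant differences between groups in new caries surfaces, and a two-level survival analysis for arrest. It mentions neither the margin nor a confidence interval. It adds that "The statistical significance level for all tests will be set at 5" per cent.

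**The concern.** A significance level limits the chance of wrongly rejecting the null, and nothing else. In a non-inferiority trial the null must therefore be that the new regimen is worse by at least the margin, so that the level limits false claims of non-inferiority. If non-inferiority is itself the null, failing to reject it reads as support, and an imprecise trial supports it more easily than a precise one.

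The heading would matter little if the analysis section then stated the margin rule. It does not. An analyst who follows the protocol literally has a null of not appreciably worse, a t-test for a difference, and a 5% level. A p-value above 0.05 can then be reported as upholding the primary hypothesis. At stake is the trial's main conclusion: whether the test regimen may be described as no worse than SDF.

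**Working it through.** **Inputs.** Margin 0.8, SD 2.0, 90% power, two-sided 95% interval (one-sided 2.5%) and 133 per group, or 166 before drop-out, all from section 3.2. T-test for a difference at 5%, from section 3.5; I take it as two-sided.

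**1. Reproduce the plan's figure.** With a true difference of 0 and the normal approximation:

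n = 2 × SD² × (1.960 + 1.282)² / margin² = 2 × 4 × 10.51 / 0.64 = 131.4, so 132 per group.

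The noncentral t gives 133 (power 0.9015; 132 gives 0.8993), so 133 is reproduced. The number alone does not settle the orientation, because a two-sided test to detect a difference of 0.8 gives the same 132 by the normal approximation. What settles it is the text of section 3.2, which judges a confidence limit against a non-inferiority margin.

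**2. Standard error.** SE = 2.0 × √(2/133) = 0.245. The 95% half-width is 1.96 × 0.245 = 0.481.

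**3. The two rules on observed data** (test minus SDF; positive means more caries on test):
- Margin rule: non-inferior if observed + 0.481 < 0.8, that is, observed below 0.319.
- Non-significance read as non-inferiority: observed below 0.481 in the unfavourable direction.

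They disagree between 0.319 and 0.481. An observed excess of 0.40 has the interval −0.08 to 0.88. The t-test is not significant, yet the interval does not exclude an excess of 0.8.

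**4. Chance of concluding non-inferiority at a given true excess D.**
- Margin rule: Φ((0.8 − D)/SE − 1.96).
- Non-significant t-test: Φ(1.96 − D/SE) − Φ(−1.96 − D/SE); the second term is negligible for the values of D below.

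| Per group | SE | D | Margin rule | Non-significant t-test |
|---|---|---|---|---|
| 133 | 0.245 | 0.8 | 2.5% | 9.65% |
| 133 | 0.245 | 1.2 | 0.02% | 0.17% |
| 166 | 0.220 | 0.8 | 2.5% | 4.6% |

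For the first row: 0.8/0.245 = 3.26, and Φ(1.96 − 3.26) = 0.0965.

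**5. Dependence on precision.** The two cut-offs coincide when 1.96 × SE = 0.8 − 1.96 × SE, so SE = 0.8/3.92 = 0.204, or about 2 × 4/0.204² ≈ 192 per group at SD 2.0. At any larger SE, which includes both planned sizes, non-significance is the looser rule. It loosens further as numbers fall or the SD rises, while the margin rule stays at 2.5% for D = 0.8.

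**6. Arrest.** No margin is given, so no false-claim rate can be computed. The inconsistency is in the text: the hypothesis is one of non-inferiority, the power statement is for a difference, and the analysis has no margin.

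**The case against.** The best defence is that this is a one-word slip in a heading. Neither numbered item uses the word null, and the first opens by calling the study a non-inferiority trial. Without the heading, both read as ordinary research hypotheses. Section 3.2 shows that the primary comparison was designed in the correct orientation, so the sponsor evidently did not mean to make non-inferiority the default. A separate statistical analysis plan, not seen here, may also state the rule.

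Much of this stands. The slip reading is plausible, the intended primary orientation can be inferred from section 3.2, and no sample-size figure is wrong. But section 3.2 describes only how the number was reached, and only for the primary outcome. The section that says what will be tested omits the margin, and the arrest hypothesis has no margin anywhere in the protocol.

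A reader might go further and infer that, with non-inferiority as the null, it would be retained 95% to 97.5% of the time at a true excess of 0.8, and 51% to 63% of the time at 1.2. Those figures belong to a one-sided test of whether the excess is greater than 0.8, with non-rejection counted as success. The protocol specifies no such test. Under the t-test that it does name, the figures are about 10% and 0.2%.

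**Conclusion.** The point holds in a limited form. The hypotheses section states both hypotheses in the reverse of the orientation used for the primary sample size, and section 3.5 does not put this right. The consequence for the primary outcome is that a non-significant difference may be taken as non-inferiority. That carries about a 10% chance of a false claim at a true excess of exactly 0.8, against 2.5%: roughly four times the intended risk.

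This rests on 133 evaluable per group, SD 2.0, normally distributed means, a two-sided 5% t-test, and non-significance being read as support. With all 166 per group retained the figure is 4.6%; with fewer than 133 or a larger SD it exceeds 10%. It measures what the wording permits and does not predict what the analysts will do. The documents do not support the inference that the trial is wrongly sized, or that non-inferiority would be accepted almost regardless of the data.

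**What to change.** **Primary item.** Drop the present heading and state both hypotheses. H0: the difference in mean new root caries surfaces over 24 months (test minus SDF) is 0.8 or more. H1: it is below 0.8. Non-inferiority is concluded only if the upper limit of the two-sided 95% confidence interval is below 0.8, which is a one-sided 2.5% test.

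**Section 3.5.** Give this rule as the primary analysis, with the margin and the direction of subtraction, and state that a non-significant t-test is not evidence of non-inferiority. Word section 3.2 with the same sign convention.

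**Secondary item.** Restate it as H0: no difference in arrest between groups, which matches the power statement in section 3.2. State that non-inferiority on arrest will not be concluded unless a margin is pre-specified. The protocol supplies none, so simply turning this item round in the same way would not be enough.

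**Cost.** Protocol wording only. The 133 per group (332 in total), the visits and the data collected are unchanged.
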